7.7.4. Management of ALT Elevation or Flare

For Cohorts 1 to 4 and 8

Participants with a serum ALT and/or AST $> 5 \times$ ULN, or ALT $> 3 \times$ ULN and total bilirubin $> 2 \times$ ULN with or without associated symptoms should be managed according to the guidance below.

Study dosing in an individual participant will be placed on hold and serum ALT or AST meeting the criteria above should be confirmed as soon as possible and ideally within 3 days of receipt of results. A clinical assessment should be performed and should include a history of recent travel and exposures, alcohol consumption, and strenuous exercise. The assessment should also include a physical examination, evaluation of the participant's mental status, and the following laboratory tests:

- Serum ALT and AST, total and direct bilirubin, GGT, INR, serum albumin, alcohol screening and urine drug screen
- If the ALT elevation is confirmed, the central clinical laboratory will conduct reflex testing for HIV, plasma HBV DNA, serology for HBV (HBsAg, hepatitis B surface antibody [HBsAb], HBeAg, and hepatitis B e antibody [HBeAb]), anti-HDV immunoglobulin (Ig)M and HDV RNA, hepatitis A virus (HAV) IgM, HCV antibody, HCV RNA, and hepatitis E virus (HEV) IgM

Participants should be monitored weekly or more frequently if clinically indicated until their ALT $< 5 \times$ ULN. They should then be monitored every 2 weeks until values return to normal. Investigational product may be restarted based on the recommendations of the SRT or if a self-limited nondrug etiology is identified.

For those with suspected drug-induced liver injury based on Hy's law (ALT or AST $> 3 \times$ ULN and total bilirubin $> 2 \times$ ULN), liver biopsy may be performed.

For Cohorts 5 to 7

Participants with a serum ALT and/or AST $> 5 \times$ ULN, or ALT $> 3 \times$ ULN and total bilirubin $> 2 \times$ ULN with or without associated symptoms should be managed according to the guidance below.

All on-treatment elevated serum ALT assessments should be confirmed as soon as possible and ideally within 3 days of receipt of results. During the visit, a clinical assessment of the participant should be performed. The assessment should include a physical examination, evaluation of the participant's mental status, and the following laboratory tests:

- Serum ALT and AST, ALP, total and direct bilirubin, GGT, INR, serum albumin, complete blood count, and urine drug screen

- If the ALT elevation is confirmed, the central clinical laboratory will conduct reflex testing for HIV, HBV DNA, qualitative HBV serology (HBeAg and HBeAb; HBsAg and HBsAb), HAV IgM, HCV RNA, anti-HDV IgM, HDV RNA, HEV IgM, antinuclear antibody, antimitochondrial antibody, smooth muscle antibody, and liver/kidney microsome

Based on the results of the confirmatory tests, the following study treatment modifications are recommended.

Table 11. ALT Elevation Monitoring and Toxicity Management

Liver Toxicity Criteria	Action
Confirmed, ALT and or AST $\geq 10 \times$ ULN without evidence of hepatic toxicity as defined below	Cohort 5 to 7: Stop investigational product. Evaluate adherence to NA therapy and review recent HBV DNA results. Evaluate for other causes of hepatotoxicity. Participant must be monitored weekly or more frequently if clinically indicated until ALT returns to nadir. Investigative product may be restarted when ALT $< 5 \times$ ULN upon discussion with medical monitor. Dosing may also be reinitiated upon the recommendations of the SRT.
Persistent ALT and or AST $> 2 \times$ baseline and $\geq 5 \times$ ULN without evidence of hepatic toxicity, as defined below	Cohorts 5 to 7: Continue investigative product. ALT should be evaluated every 2 weeks or more frequently as clinically needed, until values return to nadir.
Confirmed ALT and or AST $> 2 \times$ nadir, with evidence of hepatic toxicity, defined as any one of the following confirmed laboratory abnormalities: Total bilirubin $> 2 \times$ baseline or nadir AND $> 2.5 \text{ mg/dL}$ in the absence of Gilbert's disease Elevated INR > 0.5 above baseline AND $>$ ULN Abnormal serum albumin $> 1 \text{ g/dL}$ decrease from baseline	Cohorts 5 to 7: Permanently discontinue investigational product. Evaluate adherence to NA therapy and review recent HBV DNA results. Evaluate for etiology of ALT elevation. Participant should be monitored weekly until ALT $< 5 \times$ ULN, and total bilirubin, INR, and albumin values return to normal or baseline levels. Liver biopsy may be performed based on investigator's clinical judgment to determine etiology.

ALT = alanine aminotransferase; AST = aspartate aminotransferase; DNA = deoxyribonucleic acid; HBV = hepatitis B virus; INR = international normalized ratio; NA = nucleos(t)ide analogue; SRT = Safety Review Team; TAF = tenofovir alafenamide; ULN = upper limit of normal

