7.2.3. Liver-related Laboratory Evaluations

Liver-related abnormalities after initial study drug dosing will be examined and summarized separately for each participant population by treatment group (active group within each cohort and all participants [within population] assigned to placebo) using the number and percentage of participants who were reported to have the following laboratory test values for postbaseline measurements:

- ALT and/or AST $> 5 \times$ ULN
- ALT $> 3 \times$ ULN and Total Bilirubin $> 2 \times$ ULN
- AST $> 3 \times$ ULN and Total Bilirubin $> 2 \times$ ULN

The summary will include data from all postbaseline visits. For individual laboratory tests, subjects will be counted once based on the most severe postbaseline value. For composite endpoints, participants will be counted once when the criteria are met at the same postbaseline visit date. The denominator is the number of participants in the Safety Analysis Set who have at least 1 nonmissing postbaseline value for all relevant tests at the same postbaseline visit date.

A listing of participants who met at least 1 of the criteria above will be provided with ALT, AST, total bilirubin and alkaline phosphatase displayed in the listing for the participant's entire laboratory profile during study. Values that met criteria will be flagged in the listing.

7.3. **Body Weight, Height, and Vital Signs**

For vital signs data (systolic and diastolic blood pressure, pulse, and temperature) collected on the same date as an injection (eg, Days 1 and 57 for Cohorts 1 and 2; Days 1, 29, 57 and 85 for Cohorts 3, 4, 5, and 6; and Days 1, 29, 57, 85, 113 and 141 for Cohorts 7 and 8) both “Pre-Dose” and “Post-Dose” measurements were to be collected per protocol and will be displayed in summary tables. For displays of BMI and weight and visits where injections were not administered, only the pre-dose measurement [VSTPT_STD='VSPD' in VSPERF eCRF] will be presented in by visit displays (ie, no splitting for “pre-dose” and “post-dose” is required at any of the visits for weight or BMI or for non-injection days where vital signs were collected).

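### Protocol 7.7.4, Cohorts 1–4 and 8: the automatic dose hold omits one AST-driven pattern that meets the subsection's own Hy's-law values

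*Protocol*

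**What the plan says.** Section 7.7.4 of the protocol has separate text for Cohorts 1 to 4 and 8. Entry to the liver pathway has two limbs. The first is ALT and/or AST above 5 × ULN. The second is the combined limb: "or ALT $> 3 \times$ ULN and total bilirubin $> 2 \times$ ULN with or without associated symptoms should be managed".

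The action on entry is stated first: "Study dosing in an individual participant will be placed on hold". The enzyme result is then to be repeated promptly: "serum ALT or AST meeting the criteria above should be confirmed as soon as possible and ideally within 3 days of receipt of results". An examination and a laboratory work-up follow. Viral reflex testing has its own condition: "If the ALT elevation is confirmed, the central clinical laboratory will conduct reflex testing for HIV, plasma HBV DNA". On visit frequency: "Participants should be monitored weekly or more frequently if clinically indicated until their ALT $< 5 \times$ ULN", then every two weeks until values are normal. On resuming: "Investigational product may be restarted based on the recommendations of the SRT or if a self-limited nondrug etiology is identified".

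The subsection then gives its Hy's-law values in a sentence about optional biopsy: "law (ALT or AST $> 3 \times$ ULN and total bilirubin $> 2 \times$ ULN), liver biopsy may be performed".

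SAP Section 7.2.3 tabulates three liver categories: ALT and/or AST above 5 × ULN, the ALT-with-bilirubin combination, and a separate row for "AST $> 3 \times$ ULN and Total Bilirubin $> 2 \times$ ULN".

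**The concern.** AST counts in the first limb of the hold, in the confirmation sentence, in the Hy's-law values and in the SAP table, but not in the combined limb of the hold. For the same bilirubin above 2 × ULN, a participant with ALT at 4 × ULN is held and worked up automatically. A participant with AST at 4 × ULN and ALT at 2.5 × ULN is not.

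This is a first-in-human study, and Phase 1a inclusion criterion 11 requires ALT, AST and total bilirubin at or below ULN. The missed pattern would therefore be a clear change from screening. An automatic hold is useful because it stops the next injection before grade and relatedness have been settled, and an injection cannot be withdrawn once given. The hold can act only before the last dose: Day 57 in Cohorts 1 and 2, Day 85 in Cohorts 3 and 4, Day 141 in Cohort 8 (Section 6.5). After that, only work-up and monitoring are affected.

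**Working it through.** The plan gives no figure to reproduce, so the check compares the rules as logical conditions. All values are multiples of ULN and TB is total bilirubin.

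**Rules**

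- Hold (7.7.4, Cohorts 1–4 and 8): (ALT > 5 or AST > 5) or (ALT > 3 and TB > 2)
- Hy's-law values (same subsection): (ALT > 3 or AST > 3) and TB > 2
- SAP 7.2.3, union of three rows: (ALT > 5 or AST > 5) or (ALT > 3 and TB > 2) or (AST > 3 and TB > 2)

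**Grid.** The printed cut-points give 3 ALT classes (≤ 3, > 3 to 5, > 5), 3 AST classes (the same) and 2 TB classes (≤ 2, > 2): 3 × 3 × 2 = 18 combinations.

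**Counts**

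- Hold, first limb: ALT > 5 gives 1 × 3 × 2 = 6. AST > 5 with ALT ≤ 5 gives 2 × 1 × 2 = 4. Subtotal 10.
- Hold, combined limb: it adds ALT > 3 to 5 with AST ≤ 5 and TB > 2, which is 1 × 2 × 1 = 2. Total held: 10 + 2 = 12.
- Hy's-law values: of the 9 combinations with TB > 2, all except ALT ≤ 3 with AST ≤ 3: 9 − 1 = 8.
- Hy's-law values but not held: 1, namely ALT ≤ 3, AST > 3 to 5, TB > 2.
- SAP union: 12 + 1 = 13. The extra combination is that same one.

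Example: ALT 2.5, AST 4, TB 2.5. The Hy's-law condition is true, because AST > 3 and TB > 2. The hold condition is false, because neither enzyme exceeds 5 and ALT does not exceed 3. A finer check, with each value from 0 to 12 in steps of 0.5, found the same region and nothing outside it.

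**With AST added to the combined limb.** The hold covers 13 combinations, the only addition is the missed one, and no Hy's-law combination is left out.

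**Step-down from weekly visits (ALT < 5).** Among the 12 combinations held today, ALT is already below 5 on entry in 4 (AST > 5 with ALT ≤ 5) plus 2 (the combined limb with ALT > 3 to 5), so 6 of 12. The exact value 5 is set aside. If only the trigger were changed, this would be 7 of 13.

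**Other provisions that could stop dosing**

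| Provision | What it needs |
|---|---|
| 3.3.1 | Related Grade 3 or higher AE, or confirmed, clinically significant, related Grade 3 or higher laboratory abnormality; otherwise investigator judgement |
| 3.3.3.1 | Related SAE, or two or more participants with qualifying events, or a judgement on number and severity of AEs |
| 7.7 | Mandatory report to the medical monitor; the action is then discussed and decided |
| 7.7.2, 7.7.3 | Confirmed, related Grade 3 or 4 finding. The Grade 3 rule excepts ALT and AST, so here it works through bilirubin or a clinical event |

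None is an automatic hold on these values.

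**The case against.** The strongest reply is that other provisions protect this participant. Section 7.7 requires every treatment-emergent toxicity to be brought to the medical monitor, whatever its grade or relatedness. There is time to act: injections are at least 28 days apart, and in Cohorts 3 and 4 the chemistry samples on Days 15, 43 and 71 each come 14 days before the next dose. A reader might infer that the case would go unrecognised. The documents do not support that, because notification is mandatory. What remains is that notification leads to a discussion, while the ALT-driven case leads to a hold.

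Section 7.7 also refers to uniform guidelines in Appendix 11.5, of which only the heading is visible. That is no defect in the plan, but it limits the claim to the visible text.

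The Hy's-law sentence concerns optional biopsy and can be read as also requiring clinical suspicion. That stands, yet the values printed in it still include the AST case.

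A reader might infer that the omission is a slip, since AST appears in the neighbouring provisions. The same ALT-only limb is repeated for Cohorts 5 to 7, however, and no rationale is given either way, so intent cannot be settled. SAP reporting categories also need not equal hold triggers.

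On the dependent clauses, a reader might infer that follow-up is lost once ALT falls below 5 × ULN. It is not. The rule steps down to two-weekly checks until values are normal, and Sections 7.3.2 and 7.7 separately call for follow-up of clinically significant abnormalities and AEs. The 6 of 12 describes visit frequency only. Nor can one count how many combinations miss reflex testing, because the protocol does not define an ALT elevation for that purpose. An ALT of 2 × ULN might qualify.

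**Conclusion.** The mismatch is real and narrow. In Cohorts 1–4 and 8, exactly one combination (ALT ≤ 3, AST > 3 to 5, total bilirubin > 2 × ULN) meets the protocol's Hy's-law values without an automatic hold in the visible text. The scope is the 50 planned Phase 1a participants, before their last dose. The documents give no frequency, and I expect the pattern to be rare.

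The conclusion rests on reading the trigger as printed and on Appendix 11.5 containing no hold of its own, which cannot be confirmed. The hold finding does not extend to Cohorts 5–7: the entry sentence there has the same ALT-only limb but carries no automatic hold, and Table 11 names both enzymes.

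The change should be made because it is cheap, specific and protects healthy volunteers. The documents do not show that such a participant would in fact be redosed.

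**What to change.** In the Cohorts 1–4 and 8 text of Section 7.7.4:

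1. Entry criterion: *ALT and/or AST > 5 × ULN, or ALT or AST > 3 × ULN and total bilirubin > 2 × ULN*. The confirmation sentence already covers either enzyme and needs no edit.
2. Reflex testing, as consequential wording: make it conditional on a confirmed *ALT or AST elevation*.
3. Step-down from weekly to two-weekly visits, also consequential: *ALT and AST < 5 × ULN and no entry criterion still met*.

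Edit 1 closes the gap. Edits 2 and 3 affect only work-up and visit frequency. SAP 7.2.3 needs no change. The Cohorts 5–7 entry sentence could be aligned for consistency, but this is optional.

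Detection needs no extra sampling, because ALT, AST and bilirubin are already in the scheduled chemistry panel. The costs are an occasional hold that proves unnecessary (for example muscle-derived AST with benign raised bilirubin), some additional reflex tests and some longer weekly follow-up. A hold is reversible under the existing restart provision.

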3.3. Protocol-Specific Discontinuation Criteria

GS-2829 and GS-6779 have been evaluated in nonclinical studies without any identified dose-limiting toxicity up to the highest proposed dose. In this first in human protocol, the following rules will guide early discontinuations from the study.

3.3.1. Criteria for Early Discontinuation for the Individual Participant From the Investigational Product

Administration of the investigational product should be discontinued in the following instances:

- If a participant experiences a Grade 3 or higher treatment-emergent AE (TEAE; excluding nausea, headache, measured grades of erythema and edema/induration alone) or confirmed Grade 3 or higher laboratory abnormality (except for those with a physiologic explanation for the events [eg, blood in urine occurring in a menstruating female, creatine phosphokinase elevation after strenuous exercise, triglyceride elevation that is nonfasting, etc]) considered clinically significant by the investigator and judged as related to the investigational product
- Any AE, laboratory abnormality or intercurrent illness which, in the opinion of the investigator, indicates that continued participation in the study is not in the best interest of the participant
- Participant request to discontinue for any reason
- Participant noncompliance
- Pregnancy during the study (refer to Appendix [11.4](#))
- Loss to follow-up
- Investigator discretion
- Discontinuation of the study by the sponsor

If a participant refuses to receive the remaining doses of investigational product as the result of an AE that is judged by the investigator as related to investigational product, an early termination (ET) visit should be completed, and every attempt should be made to retain the participant in the study to continue study evaluations. Following the receipt of any abnormal results believed to be related to investigational product at the ET visit, further testing should be repeated weekly or as often as deemed clinically appropriate by the investigator until the abnormality resolves, returns to baseline visit levels, or is otherwise explained.

If the participant withdraws consent from the study, the ET evaluations and/or procedures should be performed within 7 days of the decision to discontinue from the study.

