6.6. Assessments for Early Discontinuation From Investigational Product or From the Study

If a participant discontinues dosing with the investigational product (see Section [3.3](#)), for example as a result of an AE, the ET visit evaluation and/or procedures outlined in [Table 1](#), [Table 2](#), and [Table 3](#) should be performed within 7 days of last investigational product dose. If the last investigational product dose was received more than 7 days prior to decision to discontinue future dosing, the ET visit should be completed at the next scheduled study visit. Every attempt should be made to keep the participant on the study and continue to perform study-related follow-up and procedures. Evaluations indicating abnormal results believed to be related to investigational product at the ET visit should be repeated weekly or as often as deemed appropriate by the investigator until the abnormality resolves, returns to baseline visit levels, or is otherwise explained.

If a participant withdraws consent from the study, the ET visit will be their last study visit.

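### For Cohorts 1 to 4 and 8, weekly liver monitoring in Protocol 7.7.4 ends on ALT alone, so participants who enter by AST or by ALT plus bilirubin can step down too early

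*Protocol*

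**What the plan says.** Protocol 7.7.4, in the part for Cohorts 1 to 4 and 8, sets the following.

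- **Entry.** "Participants with a serum ALT and/or AST" above 5 × ULN, or ALT above 3 × ULN with total bilirubin above 2 × ULN. Dosing is put on hold, the result is to be confirmed, ideally within 3 days, and a clinical assessment and liver panel are done.
- **Weekly stage.** "Participants should be monitored weekly or more frequently if clinically indicated until their ALT" falls below 5 × ULN. AST and bilirubin are not named.
- **Second stage.** "They should then be monitored every 2 weeks until values return to normal".
- **Reflex panel.** "If the ALT elevation is confirmed, the central clinical laboratory will conduct reflex testing for HIV, plasma HBV DNA" and further viral tests. The trigger names ALT only.

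The same section defines the Hy's law pattern as ALT or AST above 3 × ULN with total bilirubin above 2 × ULN.

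Other provisions also apply. Section 3.3.1 stops product for an adverse event of sufficient grade "or confirmed Grade 3 or higher laboratory abnormality", if it is "considered clinically significant by the investigator and judged as related to the investigational product". After an early termination (ET) visit, for abnormal results believed related to product, "further testing should be repeated weekly or as often as deemed clinically appropriate by the investigator". If the last dose was more than 7 days before the decision to stop, 6.6 says that "the ET visit should be completed at the next scheduled study visit". Section 7.7 brings in the medical monitor and also refers to Appendix 11.5.

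**The concern.** The way into the rule and the way out of its weekly stage do not match. Three markers can bring a participant in, but one marker decides when weekly checks may stop. A participant with ALT at 4 × ULN and bilirubin above 2 × ULN can therefore have a lighter written schedule than one with an isolated ALT above 5 × ULN, although the first shows part of the pattern that the protocol itself treats as suspected drug-induced liver injury.

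This is a first-in-human study, and Phase 1a inclusion criterion 11 requires ALT, AST and total bilirubin at or below the ULN, so a qualifying value is a new rise. The entering event is still counted in the analysis. What sparser draws can miss is a later, worse value or, after an AST-only entry, a later AST-plus-bilirubin event. SAP 7.2.3 counts that composite only when both criteria are met on the same visit date.

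**Working it through.** **1. Entry against exit.** Values are multiples of ULN.

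| ALT | AST | Bilirubin | Enters by | ALT below 5 already at entry? |
|---|---|---|---|---|
| 6 | 2 | 1 | ALT > 5 | No |
| 2 | 6 | 1 | AST > 5 | Yes |
| 4 | 4 | 2.5 | ALT > 3 with bilirubin > 2 | Yes |

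Read literally, the last two rows have no weekly stage. Read as a sequence (weekly, then two-weekly), they have at most one weekly check if ALT stays below 5 × ULN.

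**2. Routine chemistry.** Days are from Protocol Table 2 (Cohorts 3 and 4), Protocol Table 1 (Cohorts 1 and 2) and SAP Table 3-1 (Cohort 8).

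- Cohorts 3 and 4: Days 1, 15, 29, 43, 57, 71, 85, 99, 113, then 169 and 253. All 8 gaps to Day 113 (last dose Day 85 + 28) are 14 days.
- Cohort 8: the same to Day 113, then 127, 141, 155, 169, then 225 and 309. All 12 gaps to Day 169 (last dose Day 141 + 28) are 14 days.
- Cohorts 1 and 2: Days 1, 15, 29, 57, 71, 85, 141, 225. The gap from Day 29 to Day 57 is 28 days, so a two-weekly rule does add a check at Day 43.

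Visit windows blur this. With ±1 and ±3 days on adjacent visits, a nominal 14-day gap in Cohorts 3 and 4 after Day 15 can be 10 to 18 days.

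**3. Number of checks in the 28 days after confirmation.** Weekly: 28/7 = 4. Two-weekly: 28/14 = 2. Routine chemistry in the windows above: 28/14 = 2. If monitoring draws are merged with routine visits, the extra checks are 4 − 2 = 2 (weekly), 2 − 2 = 0 (literal reading) or at most 1 (sequential reading).

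**4. Does the ET route fill the gap?** A hold is not a discontinuation, so the route applies only if dosing is stopped. Take a draw 14 days after a dose with doses still to come: Days 15, 43 and 71 in Cohorts 3 and 4, and also Days 99 and 127 in Cohort 8. The last dose was more than 7 days ago, so the ET visit falls at the next scheduled visit: Days 29, 57 and 85, and in Cohort 8 also 113 and 141, each 14 days after the draw. Weekly repeats would start only then, for related results, and at the investigator's discretion.

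**5. How many participants?** The documents give no rate. Assume p = 0.1% to 2% per participant over the study, and n = 30 planned in Cohorts 3, 4 and 8.

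- Expected cases: 30p = 0.03 to 0.6. Chance of at least one: 1 − (1 − p)^30 = 3% to 45%.
- Only in the windows of step 2, with events spread evenly over follow-up: the shares are 112/252 = 0.444 (20 participants) and 168/308 = 0.545 (10 participants). Expected: 20p(0.444) + 10p(0.545) = 0.014 to 0.29. Chance of at least one: 1 − (1 − 0.444p)^20 × (1 − 0.545p)^10 = 1.4% to 25%.

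If events cluster near dosing, the figure lies between the two ranges.

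**The case against.** The best defence is that the section is written as a sequence, that it follows ALT by design, and that other safeguards surround it. Under the sequential reading every participant starts weekly, and the second stage runs until values, in the plural, are normal, which can take in AST and bilirubin. The protocol recognises laboratory changes after exercise, and 7.7.4 asks about strenuous exercise, so leading with ALT may be deliberate. Dosing is held, a liver panel is done, the medical monitor is consulted, 7.3.2 asks for clinically significant abnormalities to be followed to resolution or stability if possible, and investigators may stop product on their own judgement.

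Much of this stands, and it limits the point in four ways.

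- A reader might infer that these participants get no weekly check at all. Only the literal reading gives that; on the sequential reading the fault is an early step-down.
- A reader might infer that frequency rests wholly on case-by-case judgement. That is not shown. Section 7.7 refers to Appendix 11.5, whose content was not readable in the copy reviewed and which may add guidance.
- A reader might infer that two-weekly checks add nothing. The match with routine chemistry is nominal. The confirmatory draw is itself extra and can move the two-weekly clock off routine days.
- A reader might take Table 11, third row (Cohorts 5 to 7), as a precedent for the whole fix. It keeps weekly checks until bilirubin, INR and albumin recover, but the only enzyme it names is ALT. It supports the bilirubin condition only.

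Nor can a late ET visit be argued from Day 99 in Cohorts 3 and 4 or Day 155 in Cohort 8, because no dose remains to be stopped on those days.

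What the defence does not answer is the mismatch itself: AST and bilirubin are the sponsor's own entry criteria, and the exit from weekly monitoring ignores both.

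**Conclusion.** The point holds as a minor one. The 7.7.4 text for Cohorts 1 to 4 and 8 permits a step-down to two-weekly checks, at once or after at most one weekly check, for participants who enter by AST only or by ALT above 3 and below 5 × ULN with raised bilirubin. The difference is 2 checks instead of 4 in 28 days on the literal reading. On the sequential reading it is at most 1 extra check over routine chemistry, against 2 under weekly monitoring. These figures rest on nominal visit days and, for the comparison with routine chemistry, on merged visits.

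Few participants, possibly none, will be affected: 0.03 to 0.6 expected in Cohorts 3, 4 and 8 at an assumed 0.1% to 2%. The entering event is counted and the analyses are descriptive, so no conclusion of the trial is threatened. The gain is in safety follow-up and in how completely later liver values are captured.

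**What to change.** In 7.7.4, for Cohorts 1 to 4 and 8:

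- Continue weekly monitoring until ALT and AST are both below 5 × ULN and, where the ALT-plus-bilirubin criterion was met, ALT is at or below 3 × ULN and total bilirubin at or below 2 × ULN.
- Then monitor every 2 weeks until ALT, AST and total bilirubin are all normal.
- Trigger the reflex panel on a confirmed ALT or AST elevation.
- Check that Appendix 11.5 agrees with the new wording.

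The cost is a change of wording in one section and about 4 − 2 = 2 extra blood draws per 28 days in the rare participants concerned, plus a reflex panel for AST-only entries. No change to the SAP is needed.

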4.3. Phase 1b Virally Suppressed CHB Participant Inclusion/Exclusion Criteria

4.3.1. Inclusion Criteria

Phase 1b participants must meet all of the following inclusion criteria at screening (or as stated otherwise) to be eligible for participation in this study:

- 1) Have the ability to understand and sign a written ICF, which must be obtained prior to initiation of study procedures.
- 2) Assigned male sex at birth or female sex at birth (and be nonpregnant and nonlactating).
- 3) Participants assigned male at birth and participants assigned female at birth and of childbearing potential who engage in heterosexual intercourse must agree to use protocol-specified methods of contraception as described in Appendix 11.4
- 4) Be aged 18 through 65 years, inclusive, at enrollment.
- 5) Have a calculated BMI of ≤ 32.0 kg/m².
- 6) Documented evidence of CHB based on one of the following:
 - a) Positive HBsAg or HBV DNA at least 6 months prior to the screening visit; OR
 - b) Historical liver biopsy consistent with CHB infection available.

- 7) Quantitative HBsAg greater than the LLOQ and ≤ 5000 IU/mL at screening.
- 8) Have no evidence of advanced fibrosis by FibroScan (defined as FibroScan < 9 kPa within 6 months of screening). If a historical FibroScan is not available, this can be done at screening.
- 9) 12-lead ECG evaluations must be without clinically significant abnormalities as assessed by the investigator.
- 10) Nondiabetic with a hemoglobin A1c $< 6.5\%$.
- 11) Must be willing and able to comply with all study requirements.
- 12) Have a calculated CL_{cr} of at least 60 mL/min (using the Cockcroft-Gault method {[Cockcroft 1976](#)}) based on serum creatinine and actual body weight as measured for:
 - Participant assigned **male** at birth:
$$\frac{(140 - \text{Age [years]}) \times (\text{Weight [kg]})}{72 \times (\text{Serum Creatinine [mg/dL]})} = CL_{cr} \text{ (mL/min)}$$
 - Participant assigned **female** at birth:
$$\frac{(140 - \text{Age [years]}) \times (\text{Weight [kg]}) \times 0.85}{72 \times (\text{Serum Creatinine [mg/dL]})} = CL_{cr} \text{ (mL/min)}$$
- 13) Alanine aminotransferase $< 3 \times$ ULN; international normalized ratio (INR) \leq ULN; albumin ≥ 3.5 g/dL; direct bilirubin $\leq 1.5 \times$ ULN; platelets within the normal limit.

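### Protocol 7.7.4, Cohorts 5 to 7: the ALT-plus-bilirubin trigger does not map onto Table 11, so some triggered participants match no row or only Continue, and no visible rule sets a default hold

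*Protocol*

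**What the plan says.** Protocol Section 7.7.4 uses one trigger for both populations: ALT or AST above 5 x ULN, or ALT above 3 x ULN with "total bilirubin $> 2 \times$ ULN with or without associated symptoms should be managed according to the guidance below".

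For Cohorts 1 to 4 and 8, that trigger brings an immediate dosing action: "Study dosing in an individual participant will be placed on hold". The same text names ALT or AST above 3 x ULN with total bilirubin above 2 x ULN as "suspected drug-induced liver injury based on Hy's law".

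For Cohorts 5 to 7, the trigger brings confirmation (ideally within 3 days of receiving the result), examination and laboratory work-up. Table 11 then gives recommended dosing actions:

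- **Stop:** "Confirmed, ALT and or AST $\geq 10 \times$ ULN without evidence of hepatic toxicity as defined below". This row has its own restart rule: "Investigative product may be restarted when ALT $< 5 \times$ ULN upon discussion with medical monitor".
- **Continue:** "Persistent ALT and or AST $> 2 \times$ baseline and $\geq 5 \times$ ULN without evidence of hepatic toxicity, as defined below".
- **Permanently discontinue:** confirmed ALT or AST above 2 x nadir together with hepatic toxicity. Hepatic toxicity means a rise in INR above a set margin, a fall in albumin, or "Total bilirubin $> 2 \times$ baseline or nadir AND $> 2.5 \text{ mg/dL}$ in the absence of Gilbert's disease".

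Phase 1b entry requires "Alanine aminotransferase $< 3 \times$ ULN" (Section 4.3.1, criterion 13). That criterion limits direct bilirubin but not total bilirubin. Phase 1a limits total bilirubin to the ULN (Section 4.2.1, criterion 11).

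**The concern.** The trigger measures bilirubin against the ULN. Table 11 measures it against the participant's own baseline or nadir and against a fixed 2.5 mg/dL. The discontinuation row adds an ALT/AST condition relative to nadir that the trigger does not contain. A participant can therefore enter the algorithm on the ALT-plus-bilirubin pattern and find no dosing instruction, or find only the instruction to continue.

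The product is meant to raise HBV-specific T cells in people with infected livers, so rising ALT with rising bilirubin is the liver pattern to watch. SAP Section 7.2.3 tabulates it for both populations. Such participants would still be confirmed, examined and tested. What is at stake is whether the default is to give no further injection until that work-up has been reviewed.

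A smaller fault is that the Continue row has no upper limit, so it also covers values for which the Stop row was written.

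**Working it through.** The plan gives no figure to reproduce. The check applies the trigger and the three rows literally. ALT and AST are in multiples of ULN, INR and albumin are unremarkable, and AST is unremarkable (also not above 2 x its nadir). Meeting either baseline or nadir is enough for the bilirubin ratio.

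**Worked cases**

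| Case | ALT (x ULN) | Total bilirubin | Trigger met | Rows matched |
|---|---|---|---|---|
| A | 1 to 4 | 1.3 to 2.4 x ULN | yes | none |
| B | 1 to 6, persistent | 1.3 to 2.4 x ULN | yes | Continue only |
| C | nadir 2.2 to 4 | any value above 2 x ULN | yes | none |
| D | 1 to 12, confirmed and persistent | 0.8 mg/dL | yes (ALT above 5) | Stop and Continue |
| E | 2.99 to 10, confirmed and persistent | no hepatic toxicity | yes (ALT above 5) | Stop and Continue |

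- A and B: 2.4 / 1.3 = 1.85, which is not above 2. The bilirubin test fails whatever the ULN in mg/dL. In A, ALT is too low for Stop or Continue. In B, 6 is at least 5 and above 2 x 1, so Continue applies.
- C: 4 / 2.2 = 1.82, which is not above 2. The discontinuation row fails on ALT whatever the bilirubin, and 4 is below the floors of the other two rows.
- D and E: with entry ALT below 3 x ULN, 2 x baseline is below 6 x ULN, so any ALT of 10 x ULN or more exceeds it. Overlap at 10 x ULN would be avoided only if baseline were 5 x ULN or more. AST has no entry limit, so the same overlap holds when baseline AST is below 5 x ULN.

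**Width of the bilirubin mismatch**

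Let baseline and nadir total bilirubin both be b x ULN.

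- For b above 1, values above 2 and up to 2b x ULN meet the trigger but not the Table 11 test, at any ULN: 2 to 2.2 for b = 1.1, 2 to 2.6 for b = 1.3, and 2 to 3.0 for b = 1.5.
- For b at or below 1, a window exists only if 2 x ULN is below 2.5 mg/dL, that is, a ULN below 2.5 / 2 = 1.25 mg/dL. The documents do not give the ULN. An assumed 1.0 gives 2.0 to 2.5 mg/dL; an assumed 1.2 gives 2.4 to 2.5 mg/dL.

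**How much of the trigger region is affected**

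The rows were evaluated over a grid: baseline ALT 0.3 to 2.9 x ULN, current ALT 3.25 to 20 x ULN, baseline bilirubin 0.4 to 1.6 mg/dL, current bilirubin 0.3 to 4.95 mg/dL. Of the grid points with ALT above 3 x ULN and bilirubin above 2 x ULN, the discontinuation row was reached by:

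- ULN 1.0 mg/dL: 598,519 of 786,352 (76%)
- ULN 1.2 mg/dL: 598,519 of 679,728 (88%)
- ULN 1.5 mg/dL: 498,457 of 519,792 (96%)

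These are shares of an unweighted grid, not expected frequencies in participants.

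**Time before the next injection**

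Injections are 28 days apart. Between-dose liver panels fall on Days 15, 43 and 71 (Protocol Table 2), and SAP Table 3-1 also lists Days 99 and 127 for Cohort 7. The nominal gap to the next dose is 14 days. At the edges of the visit windows it is 10 days (Day 16 to Day 26), or 8 days for Cohort 7 (Day 130 to Day 138).

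**The case against.** The strongest reply is that Table 11 does not stand alone and that the schedule leaves time to act.

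- Section 7.7 sends every treatment-emergent toxicity to the medical monitor for a decision, so a participant who matches no row goes to a discussion and not automatically to the next injection.
- The first bullet of Section 3.3.1 calls for discontinuation on a confirmed, related, clinically significant Grade 3 or higher laboratory abnormality, with no ALT/AST exception. The second bullet lets the investigator stop dosing in the participant's interest.
- Section 7.7.2 withholds dosing for confirmed, related Grade 3 findings. It excepts ALT and AST, but not bilirubin. Section 7.7.3 stops permanently for confirmed, related Grade 4 findings.
- With 8 to 14 days between a scheduled panel and the next injection, confirmation would normally come first.
- The bilirubin window is narrow. In case A, a single nadir below 1.2 x ULN would make 2.4 x ULN exceed twice the nadir, and the discontinuation row would apply if the ULN is above about 2.5 / 2.4 = 1.04 mg/dL.
- Baseline-relative limits for people with CHB look deliberate. The Phase 1b cohort stopping rule in Section 3.3.3.2 likewise leaves ALT rises without hepatic injury to Section 7.7.4.

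All of this stands, and it limits the size of the problem. It does not remove it. The grade-based rules need confirmation and relatedness, and the other two routes are case by case. Laboratory turnaround is not stated, and an unscheduled draw could fall closer to a dose. None of these is a default hold on the trigger, and none corrects a row that recommends continuing in case B.

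A reader might infer two stronger things. One is that the plan lets dosing go on at 10 x ULN or more. The documents do not support that: the Stop row has its own threshold and restart rule, and reading Continue over it would leave it with no purpose. The other is that the plan contains no interim hold for Cohorts 5 to 7. That cannot be stated flatly, because Section 7.7 refers to Appendix 11.5 and its content is not visible in this copy.

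**Conclusion.** The point holds, within limits. For Cohorts 5 to 7 the ALT-plus-bilirubin trigger and Table 11 use different tests. A limited set of triggered participants is left with no row (cases A and C) or with Continue alone (case B). Most trigger combinations examined do reach permanent discontinuation. The partial backstops and the dosing interval reduce the risk further, but no visible rule sets the default hold that Phase 1a has on the same trigger.

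The overlap of Continue with Stop at 10 x ULN or more is a wording fault only, since Stop would be read to prevail.

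The documents do not allow an estimate of how often this would occur. The conclusion rests on a literal reading of Table 11, on unremarkable INR and albumin in cases A and B, and, for participants with baseline bilirubin at or below the ULN, on an assumed ULN below 1.25 mg/dL. Cases A, B and C do not depend on the ULN. This should be fixed because it concerns a named liver-injury pattern in a first-in-human study and the remedy is cheap.

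**What to change.** Amend or clarify Table 11 in two places.

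1. Cap the Continue row at below 10 x ULN.
2. Add one row that takes precedence over Continue: ALT above 3 x ULN with total bilirubin above 2 x ULN, where the permanent-discontinuation row is not met. Action: hold dosing pending confirmation and review by the medical monitor or the SRT. The hold may be released when the bilirubin is explained, for example by Gilbert's disease, which Table 11 already exempts.

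Stop continues to apply at 10 x ULN or more. Keep the baseline and nadir multiples for ALT alone, which are reasonable when entry ALT may approach 3 x ULN.

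The cost is a one-table change and occasional extra dose holds, some of them for benign raised bilirubin. It needs no added visits or tests, and SAP Section 7.2.3 stays as it is.
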